10. STATISTICAL METHODS AND SAMPLE SIZE DETERMINATION

A statistical analysis plan (SAP) will be prepared and finalized prior to database lock. This document will provide further details regarding the definition of analysis variables and analysis methodology to address all study objectives. Any deviations in the planned analysis as stated in the protocol will be delineated in the SAP. Any deviations from the SAP will be reported in the clinical study report. A data review will be conducted prior to database lock.

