If at least one model is statistically significant, then we will reject the null hypothesis of a flat dose response relationship over viral shedding change at Day 8, with a multiple contrast test controlled for the family-wise type I error rate at one-sided $\alpha = 5\%$.

After rejecting the null hypothesis, the statistically significant model(s) from the above candidate set are selected as reference models. The dose-response relationship is estimated using model average technique to generate the new estimates.

The target dose(s) can be estimated from the average model by incorporating information on the minimum clinically relevant effect and by accounting for safety.

Comparisons of active doses to placebo (90% confidence intervals [CIs] and p-values) based on the mixed effects model will be reported. These are supportive analyses of the primary endpoint to supplement the MCPMod analysis, which is the primary analysis.

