10.8. Interim Analyses

A primary analysis is planned after all patients have finished Day 8 visit or discontinued the study earlier. A decision will be made based on the interim results about whether a Phase 3 study should be initiated and which dose to be used for the Phase 3 study.

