4.3 EXPLORATORY ENDPOINTS

5 SAMPLE SIZE CONSIDERATIONS

The sample size calculation is based on the following assumptions:

- The primary endpoint “change from baseline to Day 8 in SARS-CoV-2 viral shedding” is normally distributed
- One-sided significance level $\alpha = 5\%$
- True maximum treatment effect size of BGB-DXP593 versus placebo is $-1.5 \log_{10}$ copies per mL
- Standard deviation is $3.2 \log_{10}$ copies per mL (Wang et al 2020)
- Prespecified candidate models listed in Section 6.4.1

Forty-one patients are needed with primary endpoint data per arm to provide at least 82% power to detect non-flat dose-response relationship. MCPMod approach is used. In order to ensure 41 patients per arm with primary endpoint data, at least 43 patients per arm need to be randomized to account for potential dropout rate of 5%.

The calculation has been performed using R software, version 3.6.1.

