If at least one model is statistically significant, then we will reject the null hypothesis of a flat dose response relationship over viral shedding change at Day 8, with a multiple contrast test controlled for the family-wise type I error rate at one-sided $\alpha = 5\%$. A one-sided p-value that corresponds to the most significant model will be calculated.

Bootstrap method with treatment effect resamples is used to induce dose-response relationship. Four candidate models (E_{max}, sigE_{max}, Quadratic, and Linear) are fitted and the one with lowest gAIC is selected separately for each resample. The target dose(s) can be estimated from the average model using bootstrap method by incorporating information on the target treatment effect and by accounting for safety. Denote by U_d the upper 0.95 percentile of confidence limit of the predicted mean value p_d at dose d based on the dose-response relationship, where $d = d_1$ (placebo), d_2 (5mg/kg), d_3 (15mg/kg), and d_4 (30mg/kg). The target dose can be found by

$$TD = \operatorname{argmin}_{d \in \{d_1, d_k\}} \{p_d < p_{d_1} + \Delta, U_d < p_{d_1}\}$$

where $k = 1, 2, 3$, and 4. The target treatment effect, Δ , is set to $-1 \log_{10}$ copies/ml.

Comparisons of active doses to placebo (90% confidence intervals [CIs] and p-values) based on the mixed effects model will be reported. These are supportive analyses of the primary endpoint to supplement the MCPMod analysis, which is the primary analysis.

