8 CHANGES IN THE PLANNED ANALYSIS

Not applicable.

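### The SAP's target-dose rule omits the protocol's condition that the contrast test first reject; read literally, at planning values its clauses are met in about 11% of flat-curve trials, against about 5% with the condition

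*SAP*

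**What the plan says.** **Protocol 10.2.1** sets an order. The multiple contrast test comes first. Then: "After rejecting the null hypothesis, the statistically significant model(s) from the above candidate set are selected as reference models". The dose-response curve is a model average built on those reference models, and the target dose is read from that average. If no model is significant, there is no reference model and so no target dose.

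**SAP 6.4.1** keeps the rejection rule and adds a p-value for the most significant model. A new paragraph then begins "Bootstrap method with treatment effect resamples is used to induce dose-response relationship". Four candidate families (Emax, sigEmax, quadratic, linear) "are fitted and the one with lowest gAIC is selected separately for each resample". The target dose is the smallest dose that meets two clauses:

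- Clause 1: the predicted mean p_d lies below the placebo prediction by more than the target effect of 1 log10 copies/mL.
- Clause 2: U_d lies below the placebo prediction. The SAP's definition is "Denote by U_d the upper 0.95 percentile of confidence limit of the predicted mean value p_d at dose d".

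Neither clause refers to the contrast test. Safety is to be taken into account, but no rule is given for how.

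**On changes between the documents**, Protocol Section 10 says: "Any deviations in the planned analysis as stated in the protocol will be delineated in the SAP". SAP Section 8, headed "CHANGES IN THE PLANNED ANALYSIS", declares that none apply.

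**On use of the result**, Protocol 10.8 says that a decision will be made on whether to start Phase 3 and "which dose to be used for the Phase 3 study".

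**The concern.** In MCPMod the contrast test protects the modelling step: without evidence of a dose response, no dose is estimated. The protocol says so explicitly. The SAP rewrote that part of the text and the condition is no longer there. A programmer following the SAP alone would run the bootstrap and apply the two clauses in every trial, including one whose primary test failed.

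At stake is a prespecified target dose reported from a negative trial, or a choice made after unblinding about which document governs. The visible SAP text contains no other rule for naming a dose, and the results feed the Phase 3 decision. The question is whether clause 2 does the work of the missing condition and, if it does not, how much difference the omission makes.

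**Working it through.** **Inputs.** From SAP Section 5: SD 3.2, 41 evaluable patients per arm, one-sided 5%, maximum effect -1.5. From SAP 6.4.1: the candidate shapes (Emax with ED50 2.6 and 12.5; sigEmax with ED50 10, h 4; quadratic with delta -0.022; linear) and the target effect -1. Doses are 0, 5, 15 and 30 mg/kg.

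**The plan's own figures.** Optimal contrasts for the five shapes with 4 x (41 - 1) = 160 df give a critical value of about 1.94. Under a flat curve the test then rejects in 4.8% to 5.0% of simulated trials, which agrees with the stated 5%. The same set-up gives power of 82.5% for sigEmax but 69.9% to 72.1% for the other four shapes, so the stated figure of at least 82% is matched only by the best case. That is a separate matter and does not enter the flat-curve results.

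**Hand check of clause 2.**

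- Standard error of one arm mean: 3.2/sqrt(41) = 0.50.
- One-sided 95% half-width: 1.645 x 0.50 = 0.82.
- Clause 1 already requires a gap above 1.0, and 0.82 < 1.0. Without model smoothing, a dose that meets clause 1 therefore meets clause 2 as well.
- The standard error of a difference from placebo is 0.50 x sqrt(2) = 0.71. Under a flat curve the chance that one observed difference falls below -1 is Phi(-1/0.7068) = Phi(-1.415) = 7.9%. For any of three doses, unsmoothed, it is 17.7%. Model fitting lowers this.

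**Simulation, flat curve.** Each trial draws four arm means, applies the contrast test, takes 500 parametric resamples, keeps the lowest-gAIC family in each, sets p_d to the bootstrap mean and U_d to the 95th percentile of the predictions at dose d, and applies both clauses. At SD 3.2, in 40,000 trials:

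- Clause 1 met: 4,425. Both clauses met: 4,418 (11.0%). Clause 2 removed 7.
- Both clauses met and test rejected: 2,038 (5.1%). The critical value in this run was 1.937, slightly low, and the test rejected 2,075 times (5.2%). The excess over 5% is simulation error.
- Both clauses met without rejection: 4,418 - 2,038 = 2,380, and 2,380/4,418 = 53.9%.

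Separate runs of 10,000 to 20,000 trials with critical values near 1.94 gave 11.0% without the condition and 4.7% to 4.9% with it. In those runs 55% to 57% of the doses came from trials that did not reject.

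**Sensitivity of the 11.0% to unstated details.** Bootstrap medians gave 10.9% to 11.1%; U_d at the 97.5th percentile 10.5% to 10.8%; p_d from the original fit 11.4% to 11.6%; 43 per arm 10.5%; narrower bounds on ED50 and h 10.8%.

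**Sensitivity to SD** (assumed values, flat curve, 41 per arm):

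| SD | Literal SAP | With protocol condition |
|---|---|---|
| 2.0 | 1.9% | 1.6% |
| 2.2 | 2.6% | 2.1% |
| 2.5 | 4.8% | 3.6% |
| 2.75 | 7.1% | 4.6% |
| 3.2 | 11.0% | about 5% |
| 4.0 | 16.9% | about 5% |

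A further run at SD 2.2 gave 2.4% versus 1.8%. The share of doses from failed tests also falls with SD: at 2.2 it is (513 - 423)/513 = 18%.

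**If U_d were a limit on the difference from placebo**, the rate without the condition at SD 3.2 would be 6.1% to 6.5%. In the two runs that recorded it, the rate with the condition was 4.2% to 4.3%.

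**If the drug works as planned** (five shapes, maximum effect -1.5, 10,000 trials each), the literal SAP names a dose in 80.8% to 88.3% of trials and the conditioned rule in 70.0% to 81.7%.

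**The case against.** The best defence is that the SAP is silent rather than contrary. It places the test before dose estimation, calls the analysis MCPMod, cites the protocol as reference material and declares no change. A reader may fairly conclude that the protocol's sequence still applies, and the lower rate then holds. That stands as a limit on the claim. It does not explain the model set: fitting all four families in each resample cannot be squared with using only the significant models, so at least one undeclared change exists on any reading.

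Second, the bootstrap is described as resampling treatment effects. If that means effects against placebo, U_d already carries placebo uncertainty and the literal rate is about 6% to 7%. But SAP 6.4.1 passes the average response for each treatment to MCPMod, defines U_d on the predicted mean at the dose, and compares it with a separate placebo prediction. The text favours the reading used here without settling it.

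Third, SD 3.2 comes from a trial in severe disease, while this trial excludes severe disease and adjusts for baseline viral load. A lower effective SD is plausible, and the gap nearly disappears at 2.0 to 2.2. This also stands, so the range belongs beside the 11%.

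A reader might also infer an 11% chance of taking an ineffective dose into Phase 3. The documents do not support that. Protocol 10.8 rests the decision on the results as a whole, which include the contrast-test p-value and the comparisons with placebo, and the safety consideration has no stated rule and was not modelled.

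**Conclusion.** The discrepancy is real. The protocol makes target-dose estimation conditional on rejecting H0; the SAP's rule carries no such condition, and Section 8 does not declare the difference. Clause 2 is no substitute, because it leaves out the placebo arm's error and almost never acts once clause 1 is met.

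Read literally, at planning values, the SAP's clauses are met in about 11% of flat-curve trials, against about 5% (at most 5%) with the condition. More than half of those doses come from trials that failed the primary test. These figures assume independent arm means with equal standard errors in place of the mixed-model estimates, fitting bounds that the SAP does not give (ED50 0.03 to 45 for Emax; ED50 0.5 to 45 and h 0.5 to 10 for sigEmax), and no safety screen. They hold at SD 3.2 and shrink or grow with it as tabulated.

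Two stronger readings should be resisted. The type I error of the primary test is not inflated; only the dose-naming step is affected. And fitting all four families is not shown to be worse: restricting to significant models changed the result in 2.5% to 6.2% of trials that passed the test, and neither set was uniformly better. The model set is a matter of documentation.

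**What to change.** In SAP 6.4.1, before the bootstrap sentence, state that a target dose is estimated only if the multiple contrast test rejects H0, and that otherwise the fitted curve is shown descriptively and no target dose is named. Either return to the protocol's set of significant models or list the move to all four families in Section 8. Both edits should be made before the primary-analysis database lock. No dose and no change to the target effect is proposed.

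The cost is one sentence and one reconciliation, with no new data or analysis. The statistical price is the fall shown above, from about 81-88% to about 70-82% of trials naming a dose if the drug works as planned. In 0.9% to 8.8% of all trials the withheld dose would have been the correct one under the simulated curve. The protocol already accepts that price.

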6.4.2 Secondary Endpoint Analyses

Secondary efficacy endpoints will include:

- Time-weighted average change in viral shedding as measured by RT-qPCR in nasopharyngeal swab samples from baseline to Day 15
- Change in SARS-CoV-2 viral shedding as measured by RT-qPCR in nasopharyngeal swab samples from baseline to Day 15
- Time to negative RT-qPCR in all tested samples with no subsequent positive RT-qPCR in any tested samples
- Proportion of patients requiring hospitalization due to worsened COVID-19
- Time to resolution of all COVID-19-related symptoms
- All-cause mortality rate at Day 29

The time-weighted average change in viral shedding as measured by RT-qPCR in nasopharyngeal swab samples from baseline to Day 15 is defined as:

$$\frac{\sum_{i=a}^{b-1} [0.5 \times (Y_i + Y_{i+1}) \times (t_{i+1} - t_i)]}{t_b - t_a}$$

where Y_i is the change from baseline in viral shedding at Visit i , t is the time at the specified timepoint (the actual study day), a is the baseline assessment at Day 1, and b is the last assessment at or prior to Day 15 visit. Analysis of covariance (ANCOVA) model with corresponding baseline viral shedding, disease severity at baseline, and treatment as covariates will be used. Comparisons of active doses to placebo (90% CIs and p-values) will be provided.

The same MMRM analysis for primary endpoint will be used to analyze the change in SARS-CoV-2 viral shedding from baseline to Day 3 and Day 15. Comparisons of active doses to placebo (90% CIs and p-values) will be provided.

[figure not shown]
The negative RT-qPCR is defined as the value that is below the lower limit of detection. Kaplan-Meier method will be used to assess the time to negative RT-qPCR. The corresponding quartiles (including the median) will be reported and a two-sided 90% CI of median, if estimable, will be constructed with a generalized Brookmeyer and Crowley method for each dosing group. Patients who have died prior to experiencing the event of interest will be censored on the day of data cutoff. Patients for whom the RT-qPCR value is still positive by the time of end of study visit or data cutoff, whichever comes first, will be censored on the last RT-qPCR sample date.

[figure not shown]
The number of patients who require hospitalization due to worsened COVID-19 will be counted. Corresponding proportion will be derived and a two-sided binomial exact 90% CI of proportion will be constructed.

Time to resolution of all COVID-19-related symptoms is defined as the days from randomization to the first day when all symptoms were resolved. Kaplan-Meier method will be used to assess the time to resolution of all COVID-19 related symptoms. The corresponding quartiles (including the median) will be reported and a two-sided 90% CI of median, if estimable, will be constructed with a generalized Brookmeyer and Crowley method for each dosing group. Patients who have died prior to experiencing the event of interest will be censored. Their follow-up length will be arbitrarily set as (data cutoff date – first patient in date). This approach is to count death as the worst possible outcome without possibility of recovery. Patients who have ongoing symptoms will be censored at the time of end of study visit or data cutoff, whichever comes first.

[figure not shown]
Kaplan-Meier method will be used to assess all-cause mortality rate at Day 29. A two-sided 90% CI of this rate, if estimable, will be constructed using the Greenwood's formula. Patients who do not die will be censored at the time of end of study visit or data cutoff, whichever comes first .

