8.6. Visit Windows

A visit window of ± 1 day is allowed for visits at Day 5, Day 8, and Day 15, ± 2 days is allowed for visits at Day 22 and Day 29, ± 3 days is allowed for visits at Day 57 and Day 85, and ± 7 days is allowed for visits at Day 113 ([Appendix 1](#) and [Appendix 2](#)). All assessments will be performed on the day of the specified visit unless an acceptable time window is specified.

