17. APPENDICES

APPENDIX 1. SCHEDULE OF ASSESSMENTS

Period	Screening ^a		Treatment		Follow-up ^b									
	Day -3 to -1	Day 1 Predose	Day 1 2-hour postdose	Day 1	Day 3	Day 5	Day 8	Day 15	Day 22	Day 29	Day 57	Day 85	Day 113/EOS Visit ^c	Day 31 Safety Follow-up Visit ^d
Visit Window (day)			±1 hour			±1	±1	±1	±2	±2	±3	±3	±7	±3
Informed consent ^e	X													
Inclusion/exclusion criteria ^f	X													
Demography/Prior medications	X													
Medical history	X													
Review SARS-CoV-2 results ^g	X													
Randomization ^h		X												
Study drug administration ⁱ				X										
Safety assessment														
Vital signs/height and weight ^j	X	X	X	X	X		X	X		X		X	X	X
Complete physical examination ^k	X													
Targeted physical examination ^l		X			X		X	X		X		X	X	X
12-lead ECG ^m	X	X	X							X		X	X	
Adverse event ⁿ	X	X	X		X		X	X		X		X	X	X
Concomitant medication	X	X	X		X		X	X		X		X	X	X
Efficacy assessment														
RT-qPCR for SARS-CoV-2 (nasopharyngeal swab)		X			X		X	X						

Period	Screening ^a	Treatment		Follow-up ^b										
		Day -3 to -1	Day 1 Predose	Day 1 2-hour postdose	Day 3	Day 5	Day 8	Day 15	Day 22	Day 29	Day 57	Day 85	Day 113/EOS Visit ^c	Day 31 Safety Follow-up Visit ^d
Visit Window (day)				±1 hour		±1	±1	±1	±2	±2	±3	±3	±7	±3
RT-qPCR for SARS-CoV-2 (saliva ^u)			X		X	X	X	X						
RT-qPCR for SARS-CoV-2 (blood)			X		X	X	X	X						
WHO 8-point ordinal scale ^o			X		X	X	X	X	X					
COVID-19-related symptoms ^p /Disease severity ^p	X		X		X	X	X	X	X					
Laboratory assessments														
Hematology ^q	X ^r				X		X	X			X			
Chemistry ^q	X ^r				X		X	X			X			
Coagulation ^q	X ^r				X		X	X			X			
Urinalysis ^q	X ^r						X				X			
Pregnancy test ^s	X ^r										X		X	
PK blood sampling														
ADA blood sampling														
SARS-CoV-2 serology sampling ^t		X												
			■		■		■	■					■	

See Appendix 2

See Appendix 2

Abbreviations: ADA, antidrug antibody; COVID-19, Coronavirus Disease 2019; ECG, electrocardiogram; EOS, End-of-Study; SARS-CoV-2, Severe Acute Respiratory Syndrome Coronavirus 2; IRIT, Interactive Response Technology; PK, pharmacokinetics; RT-PCR, reverse transcription-polymerase chain reaction; RT-qPCR, reverse transcription-quantitative polymerase chain reaction; WHO, World Health Organization.

^a If the site is able to complete all the screening procedures, randomization, and study treatment in 1 day, the screening assessments can be combined with the Day 1 assessments

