- b Telehealth/remote nurse home visits will be permitted after Day 1 visit (treatment)/discharge from the hospital if circumstances prevent visits to the clinic. Day 5, Day 22, and Day 57 visits will be performed by phone/video.
- c The EOS Visit will be conducted within 7 days after a premature study discontinuation. The Day 113 visit is the EOS Visit for patients who complete all the previously planned study visits.
- d The Safety Follow-up Visit is only for patients who prematurely discontinue the study within 30 days after study treatment. The Safety Follow-up Visit will be conducted at 30 days (\pm 3 days) after study treatment (Day 31 [\pm 3 days]). If the premature discontinuation from study occurs within 7 days prior to Day 31 (\pm 3 days), the Safety Follow-up Visit can be combined with the EOS Visit or the Day 29 visit, as appropriate.
- e Written informed consent must be obtained before performing any study-specific procedures. Consent must be obtained using the current version of the form approved by the Independent Ethics Committee (IEC)/Institutional Review Board (IRB). The consent can be obtained via remote consent if approved by local IRB.
- f Follicle-stimulating hormone (FSH) and estradiol assessments will be performed in female patients who are $<$ 55 years of age with no spontaneous menses for \geq 12 months to identify the status of no childbearing potential (refer to [Appendix 4](#)). Historical test results are allowed.
- g Positive results of SARS-Co V-2 test (RT-PCR or other tests authorized by local regulatory authorities) \leq 72 hours prior to screening are required for confirmation of eligibility.
- h Patients enrolled will be randomized via IRT to receive placebo, BGB-DXP593 5 mg/kg, BGB-DXP593 15 mg/kg, or BGB-DXP593 30 mg/kg on Day 1.
- i The dose of BGB-DXP593 will be based on the patient's actual body weight on the day of receiving the study drug (Day 1).
- j Vital signs will be monitored approximately every 15 minutes during the infusion, and then hourly till 2 hours after the infusion; the monitoring will include measurements of body temperature ($^{\circ}$ C), pulse rate, respiratory rate, saturation of oxygen (SpO₂), and blood pressure (systolic and diastolic). Pulse rate and blood pressure will be measured while the patient is in a seated or supine position after resting for 10 minutes. Height will be measured at screening only and weight will be measured at Day 1 before study drug dosing.

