6.2.2 Conventions

Unless otherwise specified, the following conventions will be applied to all analyses:

- 1 year = 365.25 days. Number of years is calculated as (days/365.25) rounded up to 1 decimal place.
- 1 month = 30.4375 days. Number of months is calculated as (days/30.4375) rounded up to 1 decimal place.
- Age will be calculated as the integer part of (date of informed consent – date of birth + 1)/365.25
- P-values will be rounded to 4 decimal places. P-values that round to 0.0000 will be presented as '< 0.0001' and p-values that round to 1.000 will be presented as '> 0.9999'.
- Time-to-event or duration of event endpoints will be based on the actual date the test was obtained rather than the associated visit date.
- Missing efficacy or safety data will not be imputed unless otherwise specified.
- For laboratory results collected as > x, the value of the laboratory results will be set as x. For laboratory results collected as < x, the value of the laboratory results will be set as x divided by 2.
- For by-visit observed data analyses, percentages will be calculated based on the number of patients with non-missing data as the denominator, unless otherwise specified.
- Unscheduled measurements and retested measurements will not be included in by-visit table summaries and graphs but will contribute to the best/ worst case value where required (e.g. shift table). Listings will include scheduled, unscheduled and retest data.
- For continuous endpoints, summary statistics will include n, mean, standard deviation, median, Q1, Q3 and range (minimum and maximum).

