6.2.3 Handling of Missing Data

In general, values for missing data will not be imputed, unless methods for handling missing data are specified.

For MMRM analysis, no imputation will be performed for missing viral shredding. If a patient misses a visit, the missing data will not be imputed. The mixed effect model will handle missing data based on a likelihood method under the "missing at random" assumption.

Sensitivity analyses using method of last observation carry forward (LOCF) may be considered to assess the potential impact from missing data for MMRM in primary analysis.

Missing dates or partially missing dates will be imputed conservatively for adverse events and prior/concomitant medications/procedures. Specific rules for handling of missing or partially missing dates for adverse events and prior/concomitant medications/procedures are provided in Appendix 10.1.

By-visit endpoints will be analyzed using observed data, unless otherwise specified. For observed data analyses, missing data will not be imputed and only the observed records will be included.

Censoring rules for analyses of time-to-event endpoints are determined as in [Table 1](#).

Table 1 Censoring Rules for Analyses of Time-to-event Endpoints

No.	Situation	Date of Event or Censoring	Outcome
1	Target event documented	Date of occurrence of target event	Event
2	Multiple target events documented	Date of first occurrence of target event	Event
3	No target event or death occurred by the time of the End-of-Study Visit or data cut-off, whichever comes first	Date of the End-of-Study Visit or data cut-off, whichever comes first	Censored
4	Death and no target event prior to death	Date of data cutoff	Censored

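### The time-weighted average change to Day 15 runs only to each patient's last swab, so 2-, 7- and 14-day averages enter one ANCOVA as the same endpoint

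*SAP*

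**What the plan says.** The time-weighted average change in nasopharyngeal viral load to Day 15 is the first-listed secondary efficacy endpoint. SAP 6.4.2 and Protocol 10.2.2 give the same formula: a trapezoid sum of changes from baseline, starting at Day 1 and divided by t_b - t_a, on actual study days. Both set the upper limit the same way: "b is the last assessment at or prior to Day 15 visit".

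The SAP's model is: "Analysis of covariance (ANCOVA) model with corresponding baseline viral shedding, disease severity at baseline, and treatment as covariates will be used". Each active dose is compared with placebo by a p-value and a 90% CI.

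The Schedule of Assessments (Protocol Appendix 1) places nasopharyngeal swabs at Day 1 predose, Day 3, Day 8 and Day 15. It marks none at the End-of-Study or Safety Follow-up Visit. Day 5 is remote: "Day 5, Day 22, and Day 57 visits will be performed by phone/video". On timing, Protocol 8.6 says: "A visit window of ± 1 day is allowed for visits at Day 5, Day 8, and Day 15".

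On missing data, SAP 6.2.2 says: "Missing efficacy or safety data will not be imputed unless otherwise specified". SAP 6.2.3 attaches the likelihood-based, missing-at-random handling to the MMRM and offers an optional LOCF sensitivity analysis for the primary MMRM. Neither covers the time-weighted average.

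**The concern.** The endpoint is labelled as an average to Day 15, but its window is set by when the patient was last swabbed. A patient with no Day 15 swab is averaged over about 7 days, and one with neither a Day 8 nor a Day 15 swab over about 2 days. This applies equally to patients who stay in the study and simply miss the Day 15 swab. A missed middle swab is bridged by the trapezoid and does no such harm. With no postbaseline swab the divisor is zero, and no rule is given.

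The change is 0 at baseline by construction. On a curve that keeps falling, a shorter window gives an average nearer zero for the same patient. The ANCOVA has no term or weight for length of follow-up, so the arm comparison depends on follow-up as well as on viral load. If the amount or timing of missing swabs differs by arm, the reported differences and p-values are biased even when the drug does nothing.

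**Working it through.** The documents state no figure for this endpoint, so there is none to reproduce. They also give no viral trajectory; every curve below is an assumption.

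**Inputs.** Swab times in days from baseline are 0, 2, 7 and 14 (Appendix 1, nominal). Y(0) = 0. Planned dropout is 5% with 43 patients per arm (SAP Section 5); that 5% refers to Day 8 data, and no figure is given for Day 15.

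**Formula.** Score = sum of 0.5 x (Y_i + Y_{i+1}) x (t_{i+1} - t_i), divided by (t_b - t_a).

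**Placebo, assumed -1.0/-2.5/-4.0 log10 at Days 3/8/15.** The segments are -1.00, -8.75 and -22.75.
- Last swab Day 3: -1.00/2 = -0.50
- Last swab Day 8: -9.75/7 = -1.39
- Last swab Day 15: -32.50/14 = -2.32

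**Active, assumed -1.5/-4.0/-5.0.** The segments are -1.50, -13.75 and -31.50. The scores are -0.75, -2.18 and -3.34.

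**Full 14-day arm difference:** -3.339 + 2.321 = -1.02.

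**No drug effect (placebo curve in both arms), leavers all after Day 3.** The false difference is the gap in dropout share x (2.321 - 0.50):
- 10% versus 5%: 0.05 x 1.821 = 0.09
- 10% versus 0%: 0.10 x 1.821 = 0.18
- Equal shares with the same timing: 0

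The false difference goes against the arm that loses more patients.

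**With the assumed drug effect, leavers all after Day 3.**
- 5% in each arm: 0.95 x (-1.018) + 0.05 x (-0.75 + 0.50) = -0.98, a loss of about 4%
- 10% of active, 0% of placebo: 0.9 x (-3.339) + 0.1 x (-0.75) + 2.321 = -0.76
- 0% of active, 10% of placebo: -3.339 - [0.9 x (-2.321) + 0.1 x (-0.50)] = -1.20

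**Sensitivity to the curve.** Score by last swab, one curve at a time:

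| Assumed curve | Day 3 | Day 8 | Day 15 |
|---|---|---|---|
| Linear, -0.3 per day | -0.30 | -1.05 | -2.10 |
| Exponential to -4, time constant 5 days | -0.66 | -1.74 | -2.56 |
| Exponential to -4, time constant 2 days | -1.26 | -2.65 | -3.29 |
| Flat at -3 from Day 3 | -1.50 | -2.57 | -2.79 |
| Rebound (-2, -3, -1) | -1.00 | -2.07 | -2.04 |

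On the linear and 5-day curves, with no drug effect, 10% versus 5% loss gives a false difference of 0.09 to 0.10 if all leave after Day 3, and 0.04 to 0.05 if all leave after Day 8.

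**Arms converging by Day 15.** Keep the active curve and let placebo be -1.0/-2.5/-5.0. The 14-day difference is -3.339 + 36.00/14 = -0.768. The 7-day difference is -2.179 + 1.393 = -0.786. Equal loss after Day 8 then slightly enlarges the effect.

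**Weights for a fixed 14-day window.** Day 3: (2 + 5)/2 = 3.5. Day 8: (5 + 7)/2 = 6. Day 15: 7/2 = 3.5. Each is divided by 14; the remaining 1/14 falls on baseline, where the change is 0. Check on the placebo curve: (3.5 x -1.0 + 6 x -2.5 + 3.5 x -4.0)/14 = -32.5/14 = -2.32, as above.

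**The case against.** The strongest reply is that using all available swabs is a deliberate definition, identical in both documents, and that its consequences are small. The endpoint is secondary. SAP 6.2.4 makes no multiplicity adjustment beyond MCPMod, and target-dose selection uses the Day 8 dose-response model. The same viral measure is analysed by MMRM at Days 3, 8 and 15, so an artefact could be seen beside those results. Treatment is one infusion, patients who stop it stay on study (Protocol 7.5.1), and remote or home visits are permitted, so nothing suggests large dropout differences between arms. The 10% versus 0% case is twice the planned dropout, about four patients, all in one arm and all at the earliest point. If the sample-size SD of 3.2 log10 is borrowed for this endpoint (an assumption), the standard error of an arm difference is 3.2 x sqrt(2/43) = 0.69. The 0.18 is then about a quarter of one standard error.

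All of that stands, and it limits the size of the problem. It does not make a 2-day average and a 14-day average the same quantity.

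A reader might also infer three stronger things that the documents do not support.
- That a shorter average is always nearer zero. That needs a curve that falls or stays down; on the rebound curve a patient last swabbed on Day 8 carries no penalty.
- That equal dropout always dilutes the effect. The converging-arms case shows a slight increase.
- That the Day 8 primary analysis is affected. SAP Section 7 plans efficacy and safety at that cut but does not list this endpoint. Truncation there would follow enrolment date, which randomization should balance, so it would not be expected to create a false difference under the null.

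**Conclusion.** The point holds as a defect of definition: the score depends on follow-up length, and the plan has no rule for this endpoint when the Day 15 swab is missing. The direction and size rest on assumed curves. Where viral load keeps falling, early leavers score nearer zero; with a rebound, or if the arms converge by Day 15, the direction can vanish or reverse. Bias under the null needs missing swabs that differ by arm in amount or timing: about 0.09 log10 for 10% versus 5% after Day 3, with 0.18 as an extreme case. At the planned 5% dropout, equal in both arms, the change is about 4% on the assumed curves.

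It would be wrong to read this as misclassifying responders, since the plan has no responder category; the score is continuous. The primary endpoint analysis is unaffected. Label: cheap improvement.

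**What to change.** In SAP 6.4.2, estimate the time-weighted average from the MMRM already planned for Days 3, 8 and 15, as a fixed contrast of the visit means with weights 3.5/14, 6/14 and 3.5/14. Report each active-minus-placebo difference with its 90% CI. Every patient with a postbaseline swab then informs the same 14-day quantity under the missing-at-random assumption the plan already makes.

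Protocol 10.2.2 carries the same formula and ANCOVA. Either amend it or record the change in SAP Section 8, which now lists no changes; Protocol Section 10 requires the SAP to set out departures from the protocol's planned analysis.

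Do not drop early leavers from the ANCOVA as the main analysis. That would be a completers analysis, which removes randomized patients from the ITT set and can itself be biased. The patient-level ANCOVA may stay as a sensitivity analysis. If the endpoint is reported at the Day 8 cut, label it with its actual follow-up.

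The cost is SAP wording, one estimate statement in a model already planned, and the protocol amendment or Section 8 entry. The small downside is nominal rather than actual swab days, with a window of ±1 day at Days 8 and 15.
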